## Study Overview

### A. Study Design

**Design Overview:** We will conduct a 2-group cluster randomized trial comparing eMPI to enhanced usual care (eUC) in 22 Bronx practices serving over 10,000 children with asthma. The randomization will be at the practice level to avoid contamination. Each practice will be matched into 11 similar pairs based on size and type and then randomly assigned to either eMPI or eUC.

Provider adoption of guidelines and utilization of care in all patients (~5,000) ages 2-12 years with persistent or uncontrolled asthma from eMPI and eUC practices will be evaluated using EHR data and practice-based screening for asthma severity and control. We will also enroll a random subset of 512

caregivers of children with persistent/uncontrolled asthma from both study arms to systematically evaluate caregiver-reported child morbidity outcomes and obtain measures not available in EHR. These children will be enrolled at the time of the office visit and followed prospectively for 4 time points - 3, 6, 9, and 12 months after the initial visit - to assess clinical and process-focused outcomes.

## B. Subjects and Setting

Outpatient practices (n=22) that are part of Montefiore Health System will participate in the study (see Letter of Support). These 22 practices are located throughout the Bronx, NY, represent different practice types, and have participated in several of our prior studies (Table 3). Though there were initially 22 proposed outpatient practices, two practices were closed, two practices (FCC-B and FCC-C) were combined as a single site given that they serve patients in the same facility, and one practice was excluded given no pairing available, resulting in a total n=18 participating outpatient practices. The number of children with asthma across practices (N=10,109) of whom we estimate ~ 50% (N=5,000) to have persistent or uncontrolled asthma is sufficient to meet our sample size needs. A subset of 512 children will be recruited over 4 years (~128 participants each year) to obtain clinical outcomes data that are not in the EHR.

Table 1. Primary Care Practices*					
Site	Practice Type	Provider Type	# 2-12yr olds in practice	# 2-12yr olds with asthma	# visits for 2-12yr olds with asthma
Astor Avenue	NHC	Pediatrics	3,075	576	1,012
Bronx East	NHC	Pediatrics	4,775	884	1,516
Burke Avenue	NHC	Pediatrics/Family MD	1,102	117	196
Castle Hill	FQHC	Family MD	814	97	135
CFCC	FQHC	Pediatrics	5,791	1,144	1,824
CHCC	FQHC	Pediatrics	4,658	1,332	2,488
Co-op Bartow Ave	NHC	Pediatrics	2,485	634	1,059
Eastchester	NHC	Pediatrics	1,350	325	703
FCC - B	Hospital Clinic	Pediatrics	3,671	684	1,028
FCC - C	Hospital Clinic	Pediatrics	3,470	805	1,300
FHC	FQHC	Family MD	1,739	339	606
Grand Concourse	NHC	Pediatrics/Family MD	3,133	540	868
Grand UCC	NHC	Pediatrics/Family MD	2,950	235	262
HIP Cross County	NHC	Pediatrics/Family MD	3,058	272	385
MAP-8	Hospital Clinic	Pediatrics	2,935	631	1,551
Marble Hill	NHC	Pediatrics/Family MD	1,143	186	294
University Avenue	FQHC	Pediatrics/Family MD	1,697	344	645
Verde Clinic	NHC	Family MD	359	78	146
Wakefield	NHC	Pediatrics	354	309	600
West Farms	FQHC	Family MD	954	215	368
White Plains Road	NHC	Pediatrics/Family MD	1,204	174	273
Williamsbridge	FQHC	Family MD	1,059	188	308
TOTAL	-	-	51,776	10,109	17,567

FQHC=Federally Qualified Health Center; NHC=Neighborhood Health Center. \*Number of patients seen between 1/1/14-12/31/14

**Randomization:** Prior to participant enrollment, each practice will be matched into 11 pairs based on size of the practice and provider type (Table 1). Practices will then be randomly selected within each pair as an eMPI or a eUC site. Practices will join in 4 waves over the course of 4 years (4-6 practices/year). Each practice will remain in the study for 24 months and receive \$500 donation to thank them for participation.

**Inclusion Criteria:** The criteria listed below will apply to ~5,000 children from eMPI and eUC practices. We will obtain a waiver of consent to be able to review EHR data by practice.

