## Study Objectives

This study has the following objectives:

**1. To test the impact of eMPI on provider adoption of asthma management guidelines.** The primary outcome is a clinic-level variable measured by the proportion of visits with  $\geq 1$  guideline-based corrective actions, as indicated in the EHR (i.e., controller medication prescription or adjustment, trigger evaluation). In this analysis we will include all patients ages 2-12 years with persistent or uncontrolled asthma (~5,000).

**Hypothesis 1 (primary):** eMPI will improve provider adoption of asthma guidelines compared to eUC.

**2. To determine whether consistent use of eMPI leads to both short- and long-term improvements in clinical outcomes.** Our main clinical outcome is improvement in SFDs. Since these data are not in the EHR, we will randomly sample 512 children's caregivers from eMPI and eUC practices. Caregivers will be interviewed every 3 months to examine short- (at 3 months) and long-term (at 6-12 months) change in SFDs.

**Hypothesis 2a (secondary):** Short- and long-term improvements in SFDs will be greater in eMPI over eUC.

**Hypothesis 2b (secondary):** We also will assess if these improvements are mediated by corrective actions taken at the visit.

**3. To evaluate the process of program implementation.** We will apply the RE-AIM framework to address the intervention's Reach (the provider-level proportion of visits with corrective actions), Effectiveness (provider corrective actions and SFDs), Adoption (the pace and level of uptake of guidelines), Implementation (improvements in reach and effectiveness over successive waves), and Maintenance (sustainable use of guidelines). We will evaluate group differences in the extent of healthcare utilization and resources used (i.e., adherence to clinic follow-up visits, specialty referrals, emergency and in-patient care, OW referrals).

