### **Aim 1. To test the impact of eMPI on provider adoption of asthma management guidelines.**

The **primary outcome** is a clinic-level variable measured by the ratio of number of visits with  $\geq 1$  guideline-based corrective actions to the number of visits by patients aged 2-12 years with persistent or uncontrolled asthma at the time of visit. The **primary null hypothesis** is that there is no difference between eMPI and eUC clinics in the mean proportion of visits where the necessary corrective actions were taken. To test this null hypothesis, we will use a matched-pairs randomization (or permutation test) at the 0.05 two-tailed level of

significance. The permutation test will account for the fact that clinics (rather than providers) are randomized and that the randomization will be performed within clinic pairs. Each pair of clinics will produce a matched difference in the proportions of corrective actions, and under  $H_0$  the randomization can be viewed as attaching a random plus or minus sign. Thus there will be  $2^{11} = 2,048$  possible signed permutations, allowing a two-tailed p-value as significant as  $2/2,048 < 0.001$  (if all 11 pairs show a greater proportion of corrective actions taken by the eMPI practices). Assuming no important practice characteristics are significantly out of balance (at two-tailed  $p < 0.01$ ), the permutation test will comprise the primary analysis. If any important clinic characteristics are significantly imbalanced at  $p < 0.01$ , we will adjust for such variables in a linear regression model and report the adjusted intervention coefficient as the primary result. We will also examine for a clinic-size (or provider-type) by intervention interaction. If not significant at the 5% level, the above approach will be used to provide the primary results. If significant, we will attempt to identify factors that affect the primary outcomes and might differ between clinics (or provider types). If including such factors removes the interaction, we will quote the adjusted intervention effect from the model including such factors. If not, we will quote two intervention effects (for large and small clinics) leaving the interaction unresolved.

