**Aim 3. To evaluate the process of program implementation:** In order to evaluate the potential for dissemination of this primary care intervention, we will report specific summary measures recommended by the RE-AIM framework. We will compare the provider-level proportion of visits with corrective actions taken by the eMPI providers to that of eUC providers using the same analytic approach stated in Aim 2 (Reach). We will evaluate the impact of eMPI on guideline-based corrective actions and symptoms (*Effectiveness*). We will qualitatively describe problem solving progress that occurs in each practice as part of process of improvement, by coding the specific barriers that arise during implementation and are collected by clinic champions, and the solutions that eMPI practices identify (*Adoption*). We will report consistency with which participants in the intervention arm receive the protocol through EHR data, practice observations of the process of implementation and data collected from OW contacts with participants. Additional measures of implementation of eMPI include 1) caregivers' completion of severity/control assessments at the visit; 2) provider and caregiver receipt of prompts; 3) providers' documentation of asthma discussion (*Implementation*). We will use provider survey responses to evaluate the extent to which each intervention component was continued or modified post-study and sustained effects on the primary outcome (*Maintenance*). Using EHR records of 5,000 children across all four waves of translation, we will determine if eMPI practices will (a) reach successively higher levels of guideline-based care, (b) achieve that level more quickly, and (c) sustain use of guidelines for 18 months. The analytic approach to address this will involve a statistical model with the main effect of intervention condition, time (which represents the level of Implementation), and the indicators of waves (which will allow us to evaluate sustainability), plus all the two-way and three-way interactions. We expect to see specific three-way interaction effects involving trends in rates of guideline-based care over 24 months, with an ever steeper linear increases and less pronounced downturns seen from wave to wave, in eMPI practices vs. eUC. Guideline-based care is intended to ensure that children receive needed services in a more timely fashion. We will examine patterns of utilization by children in both groups using the EHR, including adherence to clinic visits, specialty referrals, emergency and in-patient care, and OW referrals.

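### The plan gives no randomisation or rule for the order in which pairs enter the four waves, so Aim 3's wave-to-wave gains can mix better implementation with a change in the kind of practice

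*Combined protocol and SAP*

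**What the plan says.** **What is randomised.** Section B (Subjects and Setting), under Randomization, says "each practice will be matched into 11 pairs based on size of the practice and provider type (Table 1") and then "Practices will then be randomly selected within each pair as an eMPI or a eUC site". The entry sentence follows: "Practices will join in 4 waves over the course of 4 years (4-6 practices/year"). No section says how practices or pairs are allocated to waves, or that waves are balanced on size or type. Nor does the plan say outright that both members of a pair enter in the same wave. The enrolment procedures for the caregiver subset block by site pair, which suggests it.

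**How many pairs.** The same section reduces the 22 practices, "resulting in a total n=18 participating outpatient practices". That is 9 pairs, or two to three per wave.

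**What is inferred from waves.** Study Objectives, objective 3, includes "Implementation (improvements in reach and effectiveness over successive waves"), and the RE-AIM measures repeat this. The Aim 3 paragraph of the analytic plan says the EHR data will be used to "determine if eMPI practices will (a) reach successively higher levels of guideline-based care, (b) achieve that level more quickly". Its model contains arm, time, wave indicators and all their interactions, and it expects steeper gains from wave to wave in eMPI relative to eUC. It lists no practice characteristics, although the clinic-level covariates are to be collected. It does not caution that waves are not randomised.

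**Effect modification.** Aim 1 says "We will also examine for a clinic-size (or provider-type) by intervention interaction", and provides for separate effects for large and small clinics if the interaction persists.

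**The concern.** The eMPI-eUC difference within a wave is protected by randomisation if pairs enter together. The comparison of that difference between waves is not, unless the order of entry is random or otherwise unrelated to how strongly a practice responds.

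Matching on size and provider type makes the two members of a pair alike and the pairs unlike each other, so the mix of practices can differ sharply between waves of two or three pairs. In Table 1 the listed practices range from 78 to 1,332 children with asthma. That range covers the 22 practices first proposed; the 18 that took part are not fully identified. If the effect varies with such features, which Aim 1 treats as possible, an arm-by-wave trend can arise, or a real one can be hidden, with no change in how well eMPI is implemented.

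At stake is one Aim 3 conclusion: that later waves did better because implementation improved.

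**Working it through.** **1. Inputs.**
- From the documents: 9 pairs; four waves; SD of pair differences no more than 0.20 (Aim 1 power analysis); the 11 mock pair differences in Table 6.
- Assumed: 9 pairs split 2, 2, 2, 3 (18 practices, 4-6 per wave); the SD of the true eMPI effect between pairs; the correlation *r* between that effect and a single trait that fixes entry order.

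**2. Reproduce the plan's figures.** The Table 6 differences have mean 0.2455 and SD 0.1422, which match the stated 0.246 and 0.142.

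**3. Show the mechanism on the plan's own mock data.** Put the 11 pairs into waves of 3, 3, 3 and 2 and hold every pair's effect fixed.

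| Entry order | Wave 1 | Wave 2 | Wave 3 | Wave 4 | Slope per wave |
|---|---|---|---|---|---|
| Smallest to largest effect | 0.07 | 0.23 | 0.30 | 0.45 | +12.1 points |
| Largest to smallest effect | 0.40 | 0.28 | 0.18 | 0.05 | -11.4 points |

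These orders are extremes. Under random order the average slope is 0, with a central 95% range of -7.4 to +7.7 points per wave.

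**4. Size the bias for 9 pairs.** Suppose pairs enter strictly in order of the trait. The expected standardised trait values of the nine, from the order statistics of a normal sample, are ±1.485, ±0.932, ±0.572, ±0.275 and 0.
- Wave 1 (lowest two): -(1.485 + 0.932)/2 = -1.209.
- Wave 4 (highest three): (1.485 + 0.932 + 0.572)/3 = 0.996.
- Gap: 0.996 + 1.209 = 2.205.

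Expected false change, wave 1 to wave 4 = 2.205 × *r* × (effect SD). For example, 2.205 × 0.5 × 0.10 = 0.110, or 11 points.

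Only true effect heterogeneity belongs in this formula. The planning SD of 0.20 is an upper limit on the total SD of the pair differences. That total also contains sampling error and within-pair baseline differences, whose sign is set by the arm randomisation. Neither can line up systematically with a pair-level trait. The table keeps the total SD at 0.20, varies the effect SD, and gives the simulated rejection rate of a two-sided 0.05 linear-trend test on the pair differences (7 df).

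| Effect SD | False change at r = 0.3 / 0.5 / 0.7 | Rejection rate |
|---|---|---|
| 0.05 (assumed) | 3 / 6 / 8 points | 5% / 6% / 7% |
| 0.10 (assumed) | 7 / 11 / 15 points | 6% / 9% / 13% |
| 0.20 (all of the SD) | 13 / 22 / 31 points | 11% / 23% / 49% |

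With random order the expected change is 0 and the rejection rate about 5%.

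**5. Precision under random order.** The SE of wave 4 minus wave 1 is 0.20 × √(1/2 + 1/3) = 0.183. At 95% that is 1.96 × 18.3, about ±36 points. The SE of the slope is 0.20/√12 = 0.058 per wave.

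**6. Room for adjustment.** Nine pair differences, less an intercept (1), a linear wave term (1), three-level size (2) and three-level provider type (2), leave 3 df. With wave indicators (3) in place of the linear term, 1 df is left.

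**The case against.** Five points can fairly be made on the other side.

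- **Silence is not evidence of a bad order.** A reader might infer that practices were scheduled by convenience, or that large or ready ones went first. The documents do not say so. They support only the statement that no rule is described. This stands.
- **The eUC comparator removes most confounding.** A reader might infer a simple before-and-after problem, for instance from COVID-19. If pair members enter together, shared level and calendar effects largely cancel. This stands, and leaves effect modification only.
- **The large figures are an extreme.** A reader might take 31 points as the expected bias. That needs all of the 0.20 to be true effect heterogeneity, strict ordering on one trait, and a correlation of 0.7. This stands, so the range must be shown.
- **Implementation does not rest on waves alone.** Aim 3 also lists protocol receipt, completion of the severity/control assessment, receipt of prompts and documentation of asthma discussion. The wave comparison carries no numbered hypothesis. This stands.
- **Imprecision dominates.** With an SE of about 18 points, many of the biases above are smaller than one SE. This is true, but it does not answer the point. Imprecision shows in the interval; a practice-mix bias does not, and the plan neither adjusts for it nor warns of it.

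**Conclusion.** The concern holds in a limited form. The plan describes no randomisation or rule for wave order, yet it interprets between-wave differences in the eMPI-eUC contrast as improved implementation. Its Aim 3 model contains nothing to separate this from a changing mix of practices.

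The size cannot be fixed from the documents because the true effect heterogeneity is not given. Under the assumptions above, the false wave 1 to wave 4 change is about 3-8 points for an effect SD of 0.05 and 7-15 points for 0.10. The limiting case is 13-31 points. For comparison, the planned main effect is 25 points.

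A reader might infer that the trial's main results are compromised. The documents do not support that: the primary within-pair test, Aim 2 and the other Implementation measures do not depend on wave order. The change should be made because it decides what Aim 3 may conclude from the waves.

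**What to change.** **Randomization (section B).** State that pairs not yet entered are randomly ordered into the remaining waves and that both members of a pair enter together.

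**Aim 3, if the whole order was randomised.** Test the wave trend on the pair differences by re-randomising over the permitted orders only. For 9 pairs in waves of 2, 2, 2 and 3 there are 9!/(2! 2! 2! 3!) = 7,560 arrangements if the order is unrestricted. There are fewer if it is restricted, for example to mix practice sizes, and the test must then use that smaller set.

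**Aim 3, for waves already fixed.** The text already reports the reduction to 18 practices and changes from March 2020, so this may apply to some or all waves. State how the order was set and report the wave trend as non-randomised and descriptive. Add at most a sparse sensitivity adjustment, such as one arm-by-size term, because 9 pairs cannot support full size and provider-type terms.

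**Cost.** Protocol and SAP wording, one random list, slightly less freedom in scheduling practices, and a more modest Aim 3 claim. Random order removes the systematic bias but not the wide uncertainty that comes with two or three pairs per wave.

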**(1) Physician-diagnosed asthma (based on EHR).**

**(2) Persistent or uncontrolled asthma as per clinic assessment.** Based on NHLBI guidelines, any one of the following: in past month, > 2 days/week with asthma symptoms, >2 days/week with rescue medication use, >2 days/month with nighttime symptoms, or ≥ 2 episodes in the past year that required systemic corticosteroids.

1) Mild persistent or more severe asthma severity, or poor asthma control (see definitions below). \*A different assessment of eligibility will be performed depending on whether or not the child has a current prescription for preventive asthma medication at baseline and parent reports its use. This is consistent with the EPR recommendations that make a strong distinction between classifying asthma severity (for children not using preventive medications) and assessing control (for children using preventive medications). If a child has used a preventive medication in the past, but reports no use of the medication in the prior 3 months, we will assess severity. This 3-month time frame is consistent with the length of "wash-out" time for inhaled steroids.

a) **Children not using a preventive medication at baseline:** Mild persistent to severe persistent asthma. Any 1 of the following, during the prior 4 weeks (as defined by parent interview in the waiting room and EMR review):

- i) An average of >2 days per week with asthma symptoms
- ii) >2 days per week with rescue medication use
- iii) ≥3 nights per month awakened with nighttime symptoms
- iv) Minor limitation of activity
- v) >2 episodes of asthma during the past year that have required systemic corticosteroids

b) **Children using a preventive medication at baseline:** Poor asthma control. Any 1 of the following, during the prior 4 weeks (as defined by parent interview in the waiting room):

- i) An average of >2 days per week with asthma symptoms
- ii) >2 days per week with rescue medication use
- iii) ≥2 nights per month awakened with nighttime symptoms
- iv) Some limitation of activity
- v) >2 episodes of asthma during the past year that have required systemic corticosteroids.

**(3)** Age 2 and 12 years, inclusive.

Additional inclusion criteria will apply to a subset of 512 of children whose caregivers will be interviewed to systematically evaluate experiences with the program and caregiver-reported morbidity outcomes:

- (1) Caregiver is able to speak and understand either English or Spanish. Participants unable to read will be eligible as all surveys will be administered verbally by research personnel.
- (2) Consent from the primary caregiver, caregiver permission for the child to participate as well as assent from the child (>7 years). If there are eligible siblings, they will be enrolled if logistically possible.

***Exclusion Criteria:***

- (1) The child has other significant medical conditions, such as congenital heart disease, cystic fibrosis, or other chronic lung disease, that could interfere with the assessment of asthma-related measures.

Additional exclusion criteria will apply to a subset of 512 children/caregivers as described above:

- (1) No access to a telephone to conduct follow-up surveys.
- (2) Children in foster care or other situations in which consent cannot be obtained from a guardian.

*Based on our previous studies, we anticipate <10% of children will be excluded based on these criteria.*

**Screening:** In 22 practices, clinic staff (RN/LPN) will ask caregivers of all children 2-12 years of age with asthma to complete a screening survey in EPIC Electronic Health Record (EHR) during the triage portion of their doctor visit. The screening survey questions follow national guidelines and will identify children with persistent or uncontrolled asthma (Appendix A).

**Procedures for enrollment of a subset (n=512):** Clinic staff will inform research team on days of recruitment to obtain consent and baseline assessment from a subset of children with persistent or uncontrolled asthma and their caregivers from whom additional morbidity measures (not present in the EHR) will be collected.

Enrollment goals for each practice will be based on the number of children with asthma seen at the practice. Since enrollment will occur over an extended time period, we will block enrollment by site pair to assure an equal balance of children in each group for each seasonal time period. Research staff will be present in each clinic 2-3 days/week for recruitment, until monthly enrollment goals are met for that practice. We will review the practice's schedule the day before to determine if potentially eligible participants are scheduled for a visit. Research staff will call patients with asthma ages 2-12 years and ask families to come to their appointment with physician 30-60 minutes earlier to be screened by the nursing staff for asthma severity. If eligible, the caregiver/child will be informed about the study, undergo the informed consent process and complete baseline survey prior to seeing the physician. Recruitment goals will be reviewed weekly for each practice and adjustments of staffing made as needed. Days for recruitment will vary to ensure that patients of providers who are in clinic on certain days of the week are not over- or under-sampled (see Recruitment Protocol, Appendix A). Following informed consent/assent, research staff will conduct a 10-minute survey with the primary caregiver in the waiting room to obtain *baseline measures* of enrolled participants. All survey instruments will be available in English/Spanish and questions will be read aloud. Caregivers will be offered a private location within the waiting room to complete the survey. The baseline measures include standard demographic and health history variables, healthcare utilization, quality of life, beliefs about medication and adherence (Appendix A).

**eMPI Intervention:** The eMPI components are described in Table 4 and closely mirror implementation strategies recommended by the panel of experts in implementation science for development of a tailored multilevel strategy for implementation. First, at every office visit, caregivers of children ages 2-12 years with persistent or uncontrolled asthma will be asked to complete a screening survey in EPIC Electronic Health Record (EHR) during the triage portion of their doctor visit (Appendix A). Clinic staff will review the answers with the caregiver and read the questions aloud as needed. Based on these responses, a prompt for both the provider and caregiver will be generated in EPIC EHR using a simple algorithm (Appendix B). The *provider prompt* will be delivered to the provider at each visit via EHR and include information on child's current level of asthma severity or control, controller

medication use, exposure to triggers, and specific tailored recommendations for guideline-based preventive care (e.g. for persistent asthma without controller medication, the recommendation on the prompt will include starting controller medication). For children with poor control despite being on controller medications, recommendation will include evaluation of inhaler technique and medication adherence, treatment and referral for evaluation of co-morbidities (e.g., referral to the Asthma Center for allergy and pulmonology consultations), "step-up" of medications, evaluation and counseling on triggers, and outreach worker referral (See below). The prompt will also include a recommendation for the provider to establish treatment goals with the patient and inquire about any caregiver's concerns. The prompt for the provider will be seen on the computer screen in EPIC EHR at the time of the visit allowing provider to check off the guideline-based recommended items discussed during the visit. The *caregiver prompt* will include immediate feedback on child's asthma severity/control with personally tailored information highlighting caregiver's goals and concerns. The prompt will include simplified recommendations for preventive care issues to discuss with the provider during the visit (e.g., to discuss triggers, medication concerns, need for asthma action plan (AAP) and medication administration form (MAF) for school). AAP and MAF are embedded into EPIC EHR patient chart and can be printed and given to patient to take home or to school. The caregiver prompt is based on the guideline recommendation to promote joint discussions about treatment plan and goals and will be printed for caregiver to bring to the visit. *Outreach worker* (OW)-delivered telephone-based care coordination and support will be provided by the bilingual (English/Spanish) OWs, lay people from the community who have asthma or a child with well-controlled asthma. OWs will become a practice-based resource. OWs will provide telephone-based care coordination, education and support to children who are already on controller medication but still have uncontrolled asthma and other barriers to guideline-based care (e.g., unable to fill a prescription, loss of medical insurance, poor medication adherence, gaps in caregiver knowledge despite provider education). The decision to refer family to OW service will be based on provider's assessment at any office visit. Providers will be prompted to make OW referrals for children with uncontrolled asthma as part of the guideline-based care. We estimate that 20% of children in each intervention practice will be referred to the OW. Providers will have a referral mechanism embedded within EHR to refer patients to the OW with suggestions on which children should be referred. *OW training:* OWs will be trained (4-weeks) by the PI ([name]) and Co-Is ([name], [name]) using evidence-based guidelines on asthma self-management skills, proper inhaler technique, triggers, medication use, goal setting and problem solving. The PI will oversee OWs with bi-weekly (and more often if needed) meetings to discuss cases/concerns and will listen to 20% of the recorded telephone calls to ensure the OWs deliver the sessions as intended. *OWs role:* OWs will help facilitate implementation of the guideline-based care prescribed by provider at the office visit. If referred to the OW at the initial visit, the first OW telephone call with the child's caregiver will occur within 2 weeks after the initial visit to determine any care coordination needs (e.g., assistance scheduling specialty appointments, inability to fill prescriptions) and then monthly, starting at 1-month post-initial visit for 6 months. If referred at the follow-up office visit, the same

TABLE 4. CORE ELEMENTS OF eMPI MULTI-LEVEL TRANSLATIONAL STRATEGIES

- Direct Support for Providers' Delivery of Guideline-Based Care in Practice**
  - Caregiver waiting room assessment of asthma severity and control
  - Provider prompts to deliver guideline-based corrective actions at every visit
  - Caregiver prompts to encourage discussion with provider
- Enhancements to Increase the Feasibility and Sustainability of eMPI**
  - Waiting room assessment for the prompts on Tablet PCs
  - Physician prompts in Electronic Health Record (EHR)
- Involving Clinic Staff in Promoting and Supporting Use of Guidelines**
  - Regular staff administer and survey information for prompts
  - Outreach Worker-delivered care coordination and support to ensure recommendations are followed by patients
- Building Accountability and Commitment to Guideline-Based Care**
  - Designation of clinic champion to lead practice change
  - Designation of Practice Advisory Board to monitor and guide change
- Promoting Providers' Understanding, Acceptance and Use of Guidelines**
  - Interactive seminars about asthma guidelines, pocket cards with guidelines
  - Ongoing feedback about performance improvement
  - Identification of barriers to guideline use and eMPI implementation
  - Ongoing sharing of best ideas and solutions to overcome barriers

schedule of OW calls will apply. OWs will use evidence-based educational materials that were previously adapted to the needs of our community, and focus on helping parents develop 6 key asthma management behaviors as per NHLBI guidelines and our prior research using OWs: (1) Asthma control monitoring, (2) Identifying and minimizing exposure to triggers, (3) Effectively using controller medications, (4) Using quick-relief medications, (5) Using an asthma action plan, and (6) Effectively working with the child's physician and schools on optimizing asthma care. The decision to work on specific behaviors will be tailored to caregiver needs expressed at the provider visit and based on caregiver's concerns and goals identified by the caregiver prompt. During the telephone calls, OWs will also assist with patient care activities (e.g., scheduling appointments, refer to community services for Integrated Pest Management provided by the NYC Department of Health, smoking cessation programs (NYS Smokers' Quitline), free legal services and existing on-line resources) and share information with the provider and other members of the clinical team via EHR if any concerns about patient or caregiver arise during the telephone encounters (e.g., caregiver does not have prescription for medication, child seen in ED or hospitalized). The OWs will use a Microsoft Access database to record call frequency, length, and notes taken. These calls will last ~30 minutes. OWs will also send text messages, if preferred by the caregivers, to remind about clinic appointments or schedule follow-up telephone calls.

**Translational Process within eMPI Clinics:** At each intervention clinic, there will be three phases of eMPI translation into routine practice: 1) *initiation* (3 months, intense support provided), 2) *consolidation* (3 months,

Initiation	Consolidation	Sustainability
		support available), and 3) sustainability (18 months, support as needed). During the initiation phase, the goal will be to introduce eMPI to the practice. First, we will partner with a clinic champion , a practice physician who

will also serve on our *Practice Advisory Board*. The Board will consist of ≥ 2 physicians, 1-2 nurses, 1-2 front desk and administrative staff. The Board will meet monthly during the initiation and consolidation phases to review the study protocol as it relates to the practices, discuss any provider-reported barriers to implementation and identify solutions to address these barriers using a collaborative problem solving approach. These Boards will capitalize on already existing and engaged groups created by the Bronx Ongoing Pediatric Screening in the Medical Home (BOPS) program described in the Preliminary Studies section. To initiate the planning process, we will ask Board members to complete the RE-AIM planning tool to highlight any concerns or barriers to implementation. We will engage providers in a practice improvement process by having the clinic champion discuss feedback received from individual providers and solutions at the regular clinic meetings. We will provide the champion with a tool, updated monthly, to record identified barriers to guideline implementation and ways to address them. We will also collect baseline information on provider corrective actions in EHR; assess provider self-efficacy, provider-caregiver communication, and provider competencies in guideline-based care using a validated survey (Appendix A). During month 1 of the initiation phase, we will provide *practice-level support* (e.g., pocket cards with guidelines, brief interactive seminars, local asthma resources; Appendix C) to the practices to assist providers in implementing the asthma management outlined in the NHLBI guidelines and to help remove practice and provider-level barriers to guideline implementation. The interactive seminars, developed using principles of physician behavior change and led by the PI ([name]) and co-Is ([name], pulmonologist and [name], allergist), will generate enthusiasm around prompting and empower providers to implement desired changes. The seminars will include an overview of guideline-based asthma care and orientation to the prompts, resource guides and the feedback charts. At the end of the seminar, a brief needs assessment survey will be done, and additional resources will be provided based on the needs of the individual practices. Providers will receive continuing education credit for their participation. These sessions will be coordinated by each practice's champion. We will also provide *practice-level feedback*. eMPI practices will receive monthly feedback during the initiation phase on the proportion of visits with appropriate guideline-based preventive actions, and the proportion of patients meeting goals of therapy (limited symptoms, no ED visits/hospitalizations). The feedback will be delivered to the champion who will then share it with the rest of the providers. The information will be presented graphically with other intervention practices displayed by a code for comparison. A Quality Control Tool will be used to measure and assess nurse adoption of the asthma severity/control screening. Research staff will observe nursing staff at least once during the

implementation period as they conduct the severity/control asthma screening, make note of their screening practices and provide feedback to the nursing staff and the clinic champion. During the consolidation phase, we will continue to work with site champions and practices to ensure eMPI is implemented as intended and provide support on addressing barriers or concerns. Major activities during this time will include on-going monitoring of all aspects of eMPI, feedback to sites about their performance, identification of barriers and needed resources, and Board meetings to address these impediments. Given the COVID-19 pandemic, as of March 2020, Board meetings have been restricted to telephonic or video conference call only. We will finalize a sustainability plan with each practice to ensure on-going use of guidelines. During sustainability phase, we will observe practices' continued use of guideline-based care. During this time, we will not provide regular consultations or support, but will be available to address questions and concerns that arise. This will allow us to monitor how much outside help sites require to sustain eMPI. We will provide feedback at the practices' request. We expect that eMPI practices undergoing our translational program will increase guideline-based care during a 3-month initiation period and subsequent 3-month consolidation period, and will maintain these gains over an 18-month sustainability period.

**Enhanced Usual Care (eUC) Practices** will receive a review packet of the NAEPP guidelines and educational resources for families. Children will be assessed for asthma severity and level of control at each visit as best-practice care, but active intervention components will not be provided.

